Appendix D - Trigger monitoring logs

TRIGGER MONITORING LOGS

BETEL QUIDS	HOW DO YOU FEEL?									WHAT ARE YOU DOING?
	TIME	Happy	Sad or Depressed	Relaxed	Bored	Anxious	Angry	Tired	Frustrated	
1										
2										
3										
4										
5										
6										
7										
8										
9										
10										
11										
12										
13										
14										
15										

Appendix E - Trigger management worksheet

TRIGGER MANAGEMENT WORKSHEET

How did you manage your triggers for betel quid chewing this week?

1. Continue to keep a record of your triggers for betel quid chewing and the strategies you used to deal with them.
2. This week, reduce the number of betel quids you chewed by 10% of what you chewed last week and chew only the allowed quantity and record the triggers and strategies used to deal with it.

TRIGGER

STRATEGIES

TRIGGER	STRATEGIES

Appendix F - Arecoline Fading Worksheet

ARECOLINE FADING WORKSHEET

	Day 1	Day 2	Day 3	Day 4	Day 5	Day 6	Day 7	Average number chewed per week	Percentage of reduction
Week 1									
Week 2									
Week 3									
Week 4									

*To reduce 1 quid within 2-3 days OR reduce 10% of BQ within 2-3 days

Example of Betel Quid Rate Reduction Chart for 3 Weeks

Week / Day	1	2	3	4	5	6	7	Total Reduction
Week 1	10%		10%		10%			30%
Week 2	10%		10%		10%			60%
Week 3	10%		10%		20%			100%

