Arecoline fading concept and worksheet (Appendix F) is a worksheet that utilises the concept of gradually reducing the participant's physical dependence on AN. This worksheet will serve as a guide to perform the rate reduction method prior to the quit date. Participants will be advised to reduce 1 quid in a day for 2-3 days or at a rate of reduction of 10% consumption in 2-3 days. By adhering to this rate reduction method through a close monitoring from the worksheet, participants will be able to reduce the intensity of their

withdrawal symptoms on the quit day and this will make their quitting experience less difficult. This fading concept too could be a good substitute for pharmacological approaches.

Lifestyle Change worksheets will assist the participants to make lifestyle changes which are crucial for one to remain abstinent. There are 6 questions in the **Non-Chewing Game Plan : Lifestyle Change Worksheet (Appendix I)**. The questions revolve around the lifestyle changes that the participants can make to assist them to quit the habit; namely “What will you do to make betel quid unavailable to you”, “What will you do to increase time spent in non-chewing areas or doing non-chewing activities”, “How can you get help from others while trying to quit”, “What will you do to manage stress successfully”, “What will you do from keeping from gaining weight” and “What will you do to be physically active”.

[figure not shown]
Non- Chewing Game Plan : Coping with High Risk Situation Worksheet (Appendix J) is another lifestyle change worksheet that are targeted to prepare participants for potential high risk situation that they may experience in their community and daily lives. For each specific high-risk situation that they participants can identify, description of the event, persons that they might be with, what were they doing, thinking, or feeling at the time will be asked to be recorded in the worksheet. Participant will be asked to develop and record a full set of coping strategies to deal with their situation so that they could remain not chewing in such environment. They are required to utilise the 3As (Avoid, Alter, use Alternatives) of coping mechanism skills and document it in this worksheet. This worksheet really aids in their efforts to replace chewing behaviour to an abstinent one.

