Checkpoint 3 will cater for the completion practice of trigger management log (Appendix E). This management strategies are self-control strategies that one can abide with to manage their trigger situation. In a single day, participants can experience many and varied types of triggers that lead them to chew. During the intervention, participants will only be encouraged to intervene in two or three triggers in a week. This gradual approach is so that participants can cope with the withdrawal symptoms that results from the small changes. Participants will be guided on how to systematically decide on the strategies. All strategies used and advocated by the participants should be written in the worksheet. It is best that chewers tackle the easiest trigger situations before moving to a more difficult situation. Chewers would be first consulted in this management strategies as they are the best persons who have a good sense of their situations and which that could be intervened.

Checkpoint 4 will cater for the completion practice of arecoline fading concept and worksheet (Appendix F). The rationale of this concept is to gradually reduce the participant's physical dependence on AN. This can be done through the rate reduction

method prior to the quit date. Participants will be advised to reduce 1 quid within 2-3 days or at a reduction rate of 10% BQ consumption in 2-3 days. By applying this concept, participants will be able to reduce the intensity of their withdrawal symptoms on the quit day and make their quitting experience less difficult. This fading concept can be a substitute for pharmacological approaches and can be eliminated for participants who would like to quit in a cold turkey manner on the quit date.

From **Checkpoint 2-4**, participants will be required to fill their triggers and strategies that they personally could make to manage their triggers. Participants will be given a firsthand experience on it by the facilitators guiding the participants to remember the previous day’s triggers and ways they could manage those triggers. With personalised examples and guidance, they will be more self-efficient to complete worksheets in the following days. Participants will be required to fill those worksheets for a minimum of 3-4 days. The **worksheets will be collected by facilitators on Day 5 (Friday)** of the following week. The main researcher will review the trigger logs and trigger management logs to provide a summary on Session 2.

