Checkpoint 4 will be prepared to teach participants on the **brief relaxation strategies** (Appendix G). Meditative and deep-breathing technique are taught to participants. Participants will be reminded that daily use of this relaxation procedure can help reduce chewer's overall stress level; which in return may help participants to quit chewing more easily. The participants can utilise this strategy to avoid the urges to chew and to manage their triggers. These strategies will take around 10-20 minutes and can be performed while sitting on a chair.

Checkpoint 5 will be prepared to teach participants on the **brief coping skills** (Appendix H). Without being equipped with skills to cope for stressful environment, it will be impossible of any chewer to be a permanent non-chewer. Bandura (1997) stated successful coping with high risk situation leads to increase sense of self-efficacy and determines an individual's probability of maintaining chewing abstinence. Three main coping skills will be taught to participants (3As); avoiding the trigger, altering the trigger situation and finding an alternative when the chewing trigger arise.

All checkpoints will serve to practically guide participants on their checkpoint topics. At the end of Session 2, participants will be reminded of the quit day that will be on Day 15 (the morning of the third session) and concept of arecoline fading too will be re-emphasized.

[figure not shown]

Figure 3.9 Summary of Participants' Flow on the 2nd Session of the Intervention (Day 8)

3rd Session (Day 15)

On the **3rd session of the intervention (Day 15)**, it will be the quit date for the participants. Participants will be registered at **Checkpoint 1**. Main researcher and facilitators will discuss with the participants about the potential withdrawal symptoms that they may experience. Participants will be made aware that withdrawal symptoms will only persist at most up to 2 weeks, and after that period, the symptoms will fade away and not cause any difficulty. Coping strategies to combat the withdrawal symptoms will be discussed with the participants to help prevent any relapse (**Checkpoint 2**). The main researcher and facilitators will remain supportive to the participants and not to act in a judgmental manner regardless of the individual's chewing status. Physical activities that are suitable for elderly and within the vicinity of the community will be recommended for participants to cope with the withdrawal symptoms.

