3.15 Data Management and Analysis

3.15.1 Study variables and operational definition

The baseline questionnaire used in this study contains 6 parts and their variables are as described in the following tables:

Part A – Demographics

Conceptual Definition	Operational Definition	Type of Variable	Scale of Measurement
Age	Participant's age as of last birthday	Continuous/ Numerical	Years
Gender	Participant's gender	Categorical	1- Male 2- Female
Ethnic	Participant's ethnic background	Categorical	1- Bajau 2- Dusun 3- Irranun 4- Malay 5- Chinese 6- Indian 7- Others (specify)
Marital Status	Participant's current marital status	Continuous	1- Single 2- Married 3- Widowed/ Divorcee
Education Level	Participant's highest level of education	Categorical	1- University and above 2- Diploma 3- Certificate 4- STPM/ Matriculation 5- SPM 6- PMR 7- Primary school 8- No formal education
Occupation	Participant's occupation	Continuous	1- House maid 2- Unpaid worker or home maker 3- Self employed 4- Private employee

5- Government or semi government employee

Monthly Income	Participant's monthly individual income	Continuous	1 < RM 500 2 RM 501 – RM 999 3 RM 1000 – RM 2999 4 RM 3000 - RM 4999 5 RM 5000 and above
----------------	---	------------	--

Part B – BQ Chewing Behaviour & Other Concomittant Risk Habits (Maling TH, 2016 & Tahir Z et al., 2003)

Conceptual Definition	Operational Definition	Type of Variable	Scale of Measurement
Current Chewing Status	Did the participant chewed at least 1 BQ for the past 1 week	Categorical	0- No such habit 1- Habit currently practised 2- Past habit and now has stopped
Age started chewing	What was the age the participant started chewing BQ	Continuous/ Numerical	
Years have ceased the habit (for ex-chewers)	How long the ex-chewer has ceased the BQ habit	Categorical	1- A month ago 2- 3 months ago 3- About a year ago 4- Already more than 5 years
Frequency of chewing BQ	How often current BQ chewers chewed BQ	Categorical	1- Daily 2- Two-three times a week 3- Few times a month 4- I am an occasional betel quid chewer 5- Others, please specify
Number of BQ chewed per day	Number of BQ chewed by the participants in a day	Continuous/ Numerical	
Special practice (relevant to Kota Belud)	Do participants keep their BQ in their mouths overnight	Categorical	1- Yes 2- No

Past quit attempts	If the participants have attempted quitting chewing before in their life	Categorical	1- Yes 2- No

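### The arecoline-fading instructions contradict each other and run past the Day 15 Quit Day, four to seven days ahead of the Day 22 primary assessment

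*Protocol*

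**What the plan says.** **Timing.** Section 3.10.3.2 hands out Appendices D, E and F together at Session 1 (Day 1). Sections 3.10.1.3 and 3.10.3.2 both describe fading as rate reduction done before the quit date. At Session 2, "participants will be reminded of the quit day that will be on Day 15"; Table 3.4 marks the same day. The fading worksheet is collected at Session 4, Day 18.

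**Chart.** Appendix F prints an "Example of Betel Quid Rate Reduction Chart for 3 Weeks", with running totals of 30%, 60% and 100%. The blank grid above it has four weekly rows.

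**Rates.**
- Section 3.10.1.3: "reduce 1 quid in a day for 2-3 days", or 10% in 2-3 days.
- Section 3.10.3.2, Session 1: "reduce 1 quid within 2-3 days or at a reduction rate of 10% BQ consumption in 2-3 days".
- Appendix F footnote: "To reduce 1 quid within 2-3 days OR reduce 10% of BQ within 2-3 days".
- Appendix E: "This week, reduce the number of betel quids you chewed by 10% of what you chewed last week".

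**Outcome.** Section 3.12.1 lists self-reported quitting on the follow-up questionnaire at Day 22 as a primary outcome, alongside Month 3. The only operational definition of current chewing status is in section 3.15.1, Part B: "Did the participant chewed at least 1 BQ for the past 1 week". That table is introduced as describing the baseline questionnaire. The follow-up item in Appendix M has the same wording and office code (B1) and prints no look-back period.

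**The concern.** These are instructions that intervention participants hold in their hands. One sheet schedules chewing after the day on which the sessions tell them to stop, and two sheets given out together set rates about threefold apart (10% a week against the chart's 30% a week). The programme delivered then depends on which line a participant or facilitator follows.

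The statistical interest lies in the calendar. Quit Day is one week before a primary assessment, so if the chart is followed there is little or no slack between the end of fading and the Day 22 question. Whether the chart-follower counts as quit then depends on a look-back period that the follow-up item does not state.

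**Working it through.** **1. Reproduce the chart's totals.** The steps are 10% on days 1, 3 and 5 of weeks 1 and 2, then 10%, 10% and 20% on days 1, 3 and 5 of week 3.
- Week 1: 10 + 10 + 10 = 30%.
- Week 2: 30 + 30 = 60%.
- Week 3: 60 + 10 + 10 + 20 = 100%.

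The printed totals are reproduced. The last step, 20%, is itself twice the footnote's 10%.

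**2. Put the chart on the study calendar.** Assumption: chart day 1 is study Day 1, when the sheet is handed out.

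| Study days | Cumulative cut | Intake left | Left if baseline is 10 quids/day (illustrative) |
|---|---|---|---|
| 12-14 | 60% | 40% | 4 |
| 15-16 | 70% | 30% | 3 |
| 17-18 | 80% | 20% | 2 |
| 19 on | 100% | 0% | 0 |

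Zero comes four days after Quit Day and one day after the sheet is collected. For zero on Day 15, chart day 1 would have to fall on study Day 15 - 18 = -3, before the sheet is handed out. The weekly totals alone make the same point: at the end of week 2 the chart stands at 60%.

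**3. Compare the stated percentage rates by the end of Day 14.**
- 10% of baseline every 2 days: 7 steps, so a 70% cut and 30% left.
- 10% of baseline every 3 days: 5 steps if the first is on Day 1, or 4 if it comes after three days; a 40-50% cut and 50-60% left.
- Appendix E, 10% of last week's number: one reduction gives 10%; two give 1 - 0.9² = 19%; so 81-90% left.

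None of these reaches zero by Day 15.

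**4. Compare with the Day 22 assessment.** A chart-follower last chews on Day 18, with three quid-free days (19-21) before Day 22. If a one-week look-back applies:
- window Days 15-21: chewing on 4 of 7 days, total intake 0.3 + 0.3 + 0.2 + 0.2 = 1.0 baseline day's worth;
- window Days 16-22: chewing on 3 of 7 days, total 0.3 + 0.2 + 0.2 = 0.7.

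Either way the one-quid threshold in section 3.15.1 is passed at 10 quids a day. If no look-back applies, the same person can truthfully report on Day 22 that the habit has stopped.

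**The case against.** The strongest reply is that nothing in the sessions tells anyone to chew after Day 15. Table 3.4 and Session 3 make Day 15 the quit day, and Session 4 discusses three days of quitting. The chart is labelled an example, and fading can be skipped by those who prefer to stop outright. Its stated purpose is to lessen withdrawal on Quit Day, which does not require zero intake beforehand. All of this stands, and it confines any effect to participants who follow the chart in preference to the session instruction. It does not explain why a method described as preceding the quit date is illustrated by a chart that runs past it.

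The one-quid rule also behaves better than the percentage rules. With steps from Day 1 there are 5 to 7 reductions by Day 13, so a chewer starting at 5 quids a day or fewer (7 or fewer at the faster pace) reaches zero before Quit Day. The difference in wording of that rule is weak evidence by itself: the version in section 3.10.1.3 may mean lowering the daily count by one and holding it for 2-3 days.

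A reader might infer several stronger things that the documents do not support:
- **That the one-week window defines the Day 22 outcome.** It stands in the baseline variable table; neither section 3.12.1 nor Appendix M prints it. Carrying it over is an inference from the shared item wording and code.
- **That the outcome is misclassified or biased against the intervention.** A person chewing on Days 15-18 and classed as chewing in that week is classed correctly. The result would be a diluted or delayed short-term effect.
- **That participants get different sheets.** Session 1 gives Appendices D, E and F together; the conflict is within one person's set.

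**Conclusion.** Wrong as written. Two contradictions need no assumption about the outcome: the three-week chart against a Day 15 quit date that fading is said to precede, and Appendix E's weekly 10% against 10% in 2-3 days elsewhere. On the calendar, the chart leaves 40% of intake on the eve of Quit Day and reaches zero four days after it, assuming a start on Day 1.

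The consequence for the trial is conditional. It requires that some intervention participants follow the chart over the Quit Day instruction, and that the one-week definition is applied at Day 22. If both hold, those participants count as current chewers and the Day 22 contrast is diluted. The amount cannot be computed, because the share who would follow the chart is not given. The 3-month outcome, on which the hypothesis in section 1.7 rests, is not affected by this timing. The point still matters beyond tidiness, because it governs what the intervention arm is told to do in the week before a primary assessment.

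**What to change.** Reconcile section 3.10.1.3, the Session 1 and Session 2 text of section 3.10.3.2, Appendix E and Appendix F, so that one fading rule and one end date, consistent with the stated Quit Day, appear on every sheet. Then check that the look-back used for the chewing-status item at Day 22 (section 3.12.1, section 3.15.1 Part B, Appendix M) is compatible with that end date, and state it with the follow-up item. Which schedule is right is for the investigators to decide.

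The cost is edits to two worksheets and the matching paragraphs, plus one line on the look-back. Made before the pre-test, they let the pilot, which already asks about clarity of the worksheets, try the reconciled version.

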Appendix G – Brief Relaxation Exercise

BRIEF RELAXATION EXERCISE

The goal of this relaxation exercise is to learn the difference between muscle tension and relaxation. Once that distinction is mastered, it's much easier to evoke a feeling of relaxation, even in stressful settings!

Here's how to get started:

- 1) Find a quiet, darkened room. Lie on your back or sit in a comfortable, straight-backed chair.
- 2) Slowly draw as much air as you can into your chest and release it. Do this three or four times. Then let your breathing go back to its normal rhythm. Listen to it.
- 3) Starting with your face, you are going to tighten and relax groups of muscles as you move down the body. Scrunch your face up tightly for 5 seconds, then relax it. Do this for each of these muscle groups: the neck and shoulders, the arms, the stomach and chest, the legs, and the feet. As each part of your body relaxes, let it go limp. Feel the tension leave your body. You should feel like you are floating in space.

BRIEF COPING SKILLS TRAINING

Chewing doesn't just happen automatically, though it might seem like it sometimes. There are usually triggers or events that cause you to have an urge and then to chew. These triggers can be feelings, thoughts, or situations. There are three types of *behavioral* or habit changing strategies you can use to cope with these triggers, to break up the chain of events that lead to chewing:

1. Avoid the trigger. Avoiding the trigger obviously can be the most powerful strategy. If you are not around the trigger, you will not have an urge and you will not chew. For example, if you know that having a cup of coffee is a big trigger for you, then not having a cup of coffee will decrease your desire for a betel quid. However, sometimes avoiding a trigger is not always the most practical strategy; if waking up in the morning is a trigger, you can't simply avoid waking up, as much as you might like to sometimes. That's why there are two additional types of strategies to help you manage your chewing triggers.

2. Alter the trigger situation. Think of your triggers to chew as very fixed parts of your daily routine—anything that you can do to alter that routine can help you to manage your chewing urges. What you're doing is essentially taking control of your environment so that you can control your chewing. For example, let's take that cup of coffee as a trigger. If you always drink that cup of coffee in the same place using the same cup at the same time of the day, change any one or all of those parts of the routine: change the cup you use, drink your coffee in a different chair or part of the house. The key with altering a trigger is to be creative. Use it as an opportunity to challenge yourself to outsmart the environment to give you control of your chewing.

3. Substitute something else for the betel quid when you encounter the trigger. This can be as simple as putting a piece of carrot or hard non-cariogenic food in your mouth when you want a betel quid. Again, think of this as an opportunity to be creative.

Another type of coping strategy is a **cognitive** strategy that involves changing your thoughts or telling yourself things so that you will not want to chew. These self-statements can include

- a. Reasons you want to quit
- b. Benefits of quitting
- c. Statements of determination (e.g., "I can do it")
- d. Delay statements (e.g., "only five more minutes").

NON-BQ CHEWING GAME PLAN LIFESTYLE CHANGE WORKSHEET

List specific answers to some general lifestyle changes that you can make to quit chewing and remaining a non-chewer

1. What will you do to make betel quid unavailable to you?

- a. _____
- b. _____
- c. _____

2. What will you do to increase time spent in non-chewing areas or doing non-chewing activities?

- a. _____
- b. _____
- c. _____

3. How can you get help from others while trying to quit?

- a. _____
- b. _____
- c. _____

4. What will you do to manage stress successfully?

- a. _____
- b. _____
- c. _____

5. What will you do from keep from gaining weight?

- a. _____
- b. _____
- c. _____

6. What will you do to be physically active?

- a. _____
- b. _____
- c. _____

Appendix J –Non BQ Chewing Game Plan : Coping with High Risk Situation

Worksheet

**NON-BQ CHEWING GAME PLAN
COPING WITH HIGH-RISK SITUATION
WORKSHEET**

High-Risk Situations (Week of: 1 / 2 / 3 / 4)

For each specific high-risk situation, describe the event, persons you might be with, what you might be doing, thinking, or feeling at the time.

List the specific coping strategies you will use to avoid chewing in each case.

Remember 3As: Avoid, Alter, use Alternatives

NO. HIGH-RISK SITUATIONS SPECIFIC COPING STRATEGIES

1	
2	
3	
4	
5	
6	
7	
8	
9	
10	

SOCIAL SUPPORT FOR NON-BQ CHEWING WORKSHEET

Getting support and encouragement from others while you quit and work at being a non-chewer can be very helpful. Complete this handout to help you determine what other people do that is helpful or not helpful to you and what you can do to ask them to be more helpful.

Supportive Behaviors for Nonchewing:

List behaviors from others that you consider to be helpful or supportive to your nonchewing efforts:

1. _____
2. _____
3. _____

Supportive Behaviors for Nonchewing:

List behaviors from others that you consider to be not helpful or that interfere with your efforts to quit chewing:

1. _____
2. _____
3. _____

Requesting Behavior Change from Others:

What can you ask or request from others to have them engage in more actions or behaviours that you find supportive of nonchewing?

1. _____
2. _____
3. _____

What can you ask or request from others to have them engage in fewer (or eliminate completely) behaviors that you find not helpful or interfere with your efforts to quit chewing?

1. _____
2. _____
3. _____

